3.3.2. Method of Assigning Patients to Treatment Groups

This is a single arm study all eligible participants are to be assigned to IVT brolucizumab 6 mg treatment at Baseline.

| | |
|--|----------------------------------|
| | Statistical Analysis Plan |
| | Sponsor: Novartis |
| | Protocol: CRTH258AIT04 |

The Investigator will confirm that the participant has fulfilled all the inclusion/exclusion criteria in the source documents and the appropriate page on the eCRF. The Investigator will then assign the participant to treatment.

3.3.3. Prior and Concomitant Therapy

No control drug or other treatments beyond investigational drug are included in this trial.

All medications, procedures, and significant non-drug therapies (including physical therapy and blood transfusions) administered after the participant was enrolled into the study must be recorded on the appropriate page in the electronic Case Report Form (eCRF).

During the study, standard of care or other treatments according to the Investigator's practice for wAMD and other diseases in the fellow eye are permitted at any time and must be recorded in the appropriate eCRF page. Treatment of the fellow eye must be scheduled in a way not to disturb the schedule for visits and treatments in the study eye. The fellow eye must be monitored according to routine practice and adverse events (AEs) captured in the eCRF.

Corticosteroids administered via intra-nasal, inhaled, intra-articular or non-extensive dermal route (< 20% total body surface area) are permitted during the study. For other routes of corticosteroid administration, refer to *Section 6.2.2 Prohibited medication* of the study protocol.

If cataract surgery is necessary, attempt to schedule cataract surgery \geq 7 days after the most recent study treatment. Study treatment may be resumed \geq 14 days after cataract surgery, assuming an absence of surgically related complications.

If yttrium aluminum garnet (YAG) laser is necessary, it should be performed \geq 7 days prior to the scheduled study visit.

If vitrectomy is necessary in the study eye, it should be attempted to schedule the surgery \geq 14 days after the most recent study treatment. Study treatment may be given during vitrectomy surgery if deemed necessary according to investigator's discretion.

If the subject is planning to receive a COVID-19 vaccine that is authorized by local regulation, it is recommended to receive the vaccine at least 7 days before or after the study treatment visit including Baseline (Day 1) visit.

A detailed list of prohibited medications in study eye, in fellow eye and systemic treatments is provided in *Table 6-2 Prohibited medication and procedures* of the study protocol.

| | |
|--|----------------------------------|
| | Statistical Analysis Plan |
| | Sponsor: Novartis |
| | Protocol: CRTH258AIT04 |

No rescue medication for wAMD in the study eye is foreseen. In case of lack of efficacy with investigational drug for wAMD and if the Investigator deems it is in the best interest of the patient to receive prohibited treatment in the study eye, the Investigator should follow the instructions for study treatment discontinuation or study discontinuation.

3.4. Schedule of Time and Events

The flowchart of the assessments schedule is reported in Figure 2.4-1 below.

Figure 2.4-1: Assessment schedule

| Period | Screening | Treatment | | | | | | End of Study |
|--|---------------|----------------|----|----|-----|-----|-----------------------|--------------|
| Visit Name | Screening* | Baseline Day 1 | W4 | W8 | W12 | W16 | Treatment visits | W48* |
| Visit number | 1 | 2 | 3 | 4 | 5 | 6 | 7-13 | 14 |
| Weeks | Up to 2 weeks | 1 | 4 | 8 | 12 | 16 | 20 to 44 ¹ | 48 |
| Obtain informed consent | X | | | | | | | |
| Demography | X | | | | | | | |
| Inclusion/exclusion criteria | X | X | | | | | | |
| Relevant medical history/current medical history | X | | | | | | | |
| Vital Signs ^{2,3} | X | X | X | X | X | X | X | X |
| Prior/Concomitant systemic medications | X | X | X | X | X | X | X | X |
| Prior/Concomitant ocular medications | X | X | X | X | X | X | X | X |
| Serum β-hCG Pregnancy Test ⁴ | X | | | | | | | |
| Urine Pregnancy Test ⁴ | | X | X | X | X | X | X | X |
| BCVA score (ETDRS) | X | X | X | X | X | X | X | X |
| IOP measurement ⁵ | X | X | X | X | X | X | X | X |
| Complete ophthalmic examination ^{2,6} | X | X | X | X | X | X | X | X |
| SD-OCT ⁹ | X | X | X | X | X | X | X | X |
| OCTA | X | X | X | X | X | X | X | X |

| | |
|--|---|
| | Statistical Analysis Plan |
| | Sponsor: Novartis Protocol: CRTH258AIT04 |

| Period | Screening | Treatment | | | | | | End of Study |
|--|---------------|----------------|----|----|-----|----------------|-----------------------|----------------|
| | | Baseline Day 1 | W4 | W8 | W12 | W16 | Treatment visits | |
| Visit Name | Screening* | Baseline Day 1 | W4 | W8 | W12 | W16 | Treatment visits | W48* |
| Visit number | 1 | 2 | 3 | 4 | 5 | 6 | 7-13 | 14 |
| Weeks | Up to 2 weeks | 1 | 4 | 8 | 12 | 16 | 20 to 44 ¹ | 48 |
| FA ⁹ | X | | | | | | | X |
| ICGA | X | | | | | | | X |
| Color Fundus Photography (CFP) ¹⁰ | X | X | X | X | X | X | X | X |
| EQ-5D-5L | | X | | | | | | X |
| HADS | | X | | | | | | X |
| Disease Activity Assessment ⁷ | | | | | | X | X | X |
| Study drug administration | | X | X | X | | X ⁸ | X ⁸ | X ⁸ |
| Adverse Events | X | X | X | X | X | X | X | X |

X = assessment to be recorded in the clinical database or received electronically from a vendor

* At Screening and Week 48 the fellow eye will be assessed for BCVA, ophthalmic examination, IOP, SD-OCT, OCTA, CFP, FA and ICGA. For the other visits it will be assessed according to clinical practice

¹ Treatment visits will take place every 8 or 12 weeks starting from Visit 4 (Week 8), according to Investigator's decision at each assessment visit

² Vital signs collection and/or complete ophthalmic examination are to be performed at each visit. The Investigator have to exclude the presence of any active intraocular inflammation in the study eye.

³ Vital signs include sitting blood pressure and pulse rate.

⁴ Women of childbearing potential only. A positive urine test should be confirmed by a Serum β-hCG Pregnancy test.

⁵ IOP measurement is to be performed prior and 30-60 minutes after each treatment IVT injection

⁶ Complete ophthalmic examination include slit lamp exam, IOP measurement and fundus exam, for safety assessment before and after IVT. Pupil dilation optional according to local practice.

⁷ Disease activity assessment to be performed by the Investigator based on BCVA and/or one or more anatomical parameters detected by SD-OCT among IRF, SRF, sub-RPE fluid, hemorrhage and CRT, and/or OCTA parameters and/or 3-field CFP, as per clinical practice. Of note, only which of these functional and/or anatomical parameters the Investigator considered to assess disease activity will be recorded in the eCRF.

⁸ Treatment according to Investigator's decision on treatment regimen (q12w or q8w) based on disease activity assessment.

The planned study visit schedule will be established at Baseline/Day 1 (first day of treatment) for all participants. All subsequent scheduled visits will be calculated based on the Day 1 visit date. The mandatory post-Baseline visits of the study are Week 4, Week 8, Week 12 (no injection visit), Week 16 and Week 48. After Week 16, the treatment visit intervals will be determined by the Investigator, based on the patient's disease activity.

| | |
|--|----------------------------------|
| | Statistical Analysis Plan |
| | Sponsor: Novartis |
| | Protocol: CRTH258AIT04 |

A \pm 7-day visit window is allowed, except for Baseline/Day 1. For a given protocol visit (except for Baseline), assessments can be performed on two consecutive days, provided both days are within the \pm 7-day visit window.

Treatment is intended to be administered on the day of study visit, or if this is not possible, within 3 days after the study visit at which the per-protocol assessments have taken place (except Baseline, in which case study treatment administration should occur within the next 24 hours). Two consecutive study treatments should be at least 21 days apart. For all visits, efficacy assessments and safety assessments should be performed prior to any administration of study treatment.

Missed or rescheduled visits should not lead to automatic discontinuation. Participants who prematurely discontinue the study for any reason should be scheduled for a visit as soon as possible, at which time all of the assessments listed for the final visit will be performed.

If the COVID-19 pandemic limits or prevents on-site study visits, study treatment could not be administered, and other study assessments may not be performed. Alternative methods of safety monitoring may be implemented. Depending on local regulations, site capabilities and patient's visit status in the study, phone calls or virtual contacts (e.g., teleconsulting) can be performed for safety follow-up for the duration of the pandemic, until it is safe for the participant to visit the site again.

3.5. Sample Size and Power Estimation

The sample size calculation is based on the assumption of an expected percentage of participants who have maintained the q12w regimen up to Week 48 equal to 56%, as derived from the HAWK study, and the hypothesis of a maximum percentage of not-fluid free participants out of these q12w-regimen participants at Week 48 equal to 18%. Therefore, the percentage of responders, defined as fluid-free participants who have maintained a q12w stable regimen up to Week 48, could range between 56% to 46%.

[figure not shown]
Considering a percentage of responders of 56% and a maximum width of the 95% confidence interval of 12%, 263 patients should be enrolled. Applying the rules of thumb, with 263 patients and a percentage of responders of 56%, a maximum number of 12 covariates can be included in the multivariate regression model (Harrell, 2015). As shown in Figure 2.5-1, the precision of the estimate remains stable around 12%, considering a percentage of responders ranging between 56% to 46%. Similar considerations can be made with a number of covariates that remains equal to 12.

Finally, to account for a screening failure rate of 12%, a total of approximately 300 participants should be screened in order to enroll 263 evaluable participants.

The sample size calculations were performed with nQuery 7.0.

| | |
|--|----------------------------------|
| | Statistical Analysis Plan |
| | Sponsor: Novartis |
| | Protocol: CRTH258AIT04 |

[figure not shown]
Figure 2.5-1: Precision of the estimate scenario

Since the enrolment was closed with less than 263 enrolled patients, the precision of the 95% CI will be re-computed based on the effective number of patients evaluable for the primary endpoint of the study.

Based on interim analysis, 122 enrolled patients will be available and consequently, the Figure above is recomputed according to the effective number of enrolled patients and provided below in Figure 2.5-2:

Figure 2.5-2: Precision of the estimate scenario re-computed

Based on different scenario of expected proportion between 46% to 56% and the effective number of 122 enrolled patients, the maximum width that can be observed will be of 17.74%.

| | |
|--|---|
| | Statistical Analysis Plan |
| | Sponsor: Novartis Protocol: CRTH258AIT04 |

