For what concern the LOCF approach reported in the study protocol, this approach will be maintained for the predictors to be included in the analysis of the primary endpoint since the focus is on the first visits (from baseline to Week 16) and all enrolled patients should perform these visits independently of treatment regimen that will be followed by each patient. For the secondary endpoints, LOCF approach will not be applied because after Week 16 each patient will have different scheduled of visits based on treatment regimen. The LOCF approach can be considered only until Week 16 but (1) for OCTA the number of missing data will lead to most data imputed than the one observed, (2) for SD-OCT the approach is applied in the analysis of primary endpoint, (3) for BCVA the LOCF approach will be provided until Week 16, (4) for HAD and EQ-5D-5L questionnaires the LOCF approach will not be applied since only two assessments of these questionnaires are planned in the study.

As performed for interim analysis, all analysis will be conducted on Safety population since during the interim analysis, in which all enrolled patients were considered (see section 6.6 for further details), the FAS and Safety populations include the same set of patients since per definitions of the study protocol, the FAS considered all enrolled patients who completed the baseline visit and all of them are treated and consequently all of them belong to Safety population.

The evaluation of prevalence of anxiety and depression will be performed only based on HAD questionnaire and not based in terms of treatment that patients could have received for anxiety/depression.

The following additional analysis will be included:

- SD-OCT parameters at baseline and type of predominant lesion will be also analyzed according to BCVA groups and CST groups based on changes at Week 12 in patients who performed Week 16 and were still on treatment at this timepoint.
- A graphical representation of BCVA ETDRS score and CST by means of spaghetti plot will be provided.
- Analyses on CST and BCVA will be also performed on patients with BCVA ETDRS score lower than 69 letters at baseline.

| | |
|--|----------------------------------|
| | Statistical Analysis Plan |
| | Sponsor: Novartis |
| | Protocol: CRTH258AIT04 |

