6.3. Efficacy Evaluation

6.3.1. Primary efficacy analysis

Definition of primary endpoint

The primary aim of the study is to assess which early anatomical parameters measured by multimodal imaging at each visit from Baseline to Week 16, predict in brolucizumab-treated participants with wAMD the q12w fluid-free response at Week 48.

The primary estimand of the study is to identify the q12w fluid-free predictive factors.

Patient will be classified as follows for the outcome of interest:

- **q12w fluid-free:** patients completing the treatment and the study maintaining a stable q12w regimen assigned at Week 16 up to Week 48 and without the presence of IRF and SRF at Week 48 according to SD-OCT grading.
- **not q12w fluid-free:**
 - patient who completes the treatment and the study with the presence of IRF or the presence of SRF at Week 48 according to SD-OCT grading;
 - patient who followed the q8w regimen of treatment at any time during the study (considering also who started with q12w regimen but then due to disease activity shifted to q8w regimen);
 - patient who discontinued treatment at any time after baseline since also the discontinuation from the treatment can be considered as intercurrent event and according to data handling rules should be considered as 'failure'.
 - patient who dropped out at any time after baseline since the discontinuation from the study is considered as intercurrent event and according to data handling rules should be considered as 'failure'.

The following qualitative and quantitative anatomical parameters measured by FA, ICGA, CFP and SD-OCT will be considered as potential predictive factors in the statistical model and, when measured at more than one timepoint, categories variables based on their changes between baseline and Week 16 will be created as described below:

| | |
|--|---|
| | Statistical Analysis Plan |
| | Sponsor: Novartis Protocol: CRTH258AIT04 |

| Variable | Timing of data collection | Source | Categories used in the model | Reference value for the model |
|----------------------------------|---|--|--|-------------------------------|
| Type of predominant CNV lesion | Screening | CRC grading based on SD-OCT, FA, ICGA and CFP at Screening | Type I, Type II, Type III, PCV, UNG/P or UNG/Q. Of note, Type I and PCV will be considered as unique category while UNG/P and UNG/Q will be considered as missing data. | Type I + PCV |

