NA=Not Applicable; CNV=Choroidal Neovascularization; UNG/P=Ungradable due to pathology; UNG/Q=Ungradable due to quality SHRM=Subretinal hyper reflective materia; ORT=Outer retinal tubulation; ELM=External Limiting Membrane; CST=Center Subfield Thickness; PED=Pigment Epithelial Detachment.

Of note, for each variable 'Missing' values can be present in case that images are collected but not graded by Central Reading Center (CRC) since they are collected by means of a not certificated instrument.

| | |
|--|----------------------------------|
| | Statistical Analysis Plan |
| | Sponsor: Novartis |
| | Protocol: CRTH258AIT04 |

Analysis methodology

Firstly, the proportion of patients with and without q12w fluid-free will be provided and then a descriptive summary table by q12w fluid-free and not q12w fluid-free will be provided for each variables described in table above.

A logistic models will be performed for each one of the variables listed above considering as outcome the patients' classification in q12w fluid-free and not q12w fluid-free.

Multivariable logistic model will be performed considering as outcome the patients' classification in q12w fluid-free and not q12w fluid-free and as covariates all the variables with $p<0.10$ in the previous analysis. Results of logistic models will be presented in terms of beta coefficient and standard error, Odds Ratio and relative 95% Confidence interval and p-value.

All these analyses will be performed on Safety population.

Data handling rules

In case of patients who dropped out at any time after baseline, the primary outcome cannot be evaluated since the patient status related to treatment regimen and presence of IRF o SRF at Week 48 are not observed. The dropped-out patients constitute intercurrent event and they will be considered a not q12w fluid-free at Week 48. Similarly, in case of patients who discontinued the treatment at any time after baseline, the primary outcome cannot be totally evaluated since the patient treatment regimen at q12w cannot be observed until Week 48. The patients who discontinued treatment constitute intercurrent event and they will be considered a not q12w fluid-free at Week 48.

Sensitivity of primary analysis

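### The covariate limit was not recalculated for 122 patients, and the primary model is screened at p<0.10 and fitted on the same data with no internal validation

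*SAP*

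**What the plan says.** SAP section 3.5 repeats the protocol's sample size text. For 263 patients and 56% responders, "a maximum number of 12 covariates can be included in the multivariate regression model", and the number is said to stay at 12 over a responder range of 46% to 56%. The section then deals with the shortfall. It says that "the precision of the 95% CI will be re-computed based on the effective number of patients evaluable for the primary endpoint", and for "the effective number of 122 enrolled patients, the maximum width that can be observed will be of 17.74" per cent. It gives no covariate limit for 122.

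SAP section 6.3.1 fits one logistic model for each of seven candidates: predominant CNV lesion type, sub-RPE fluid, SHRM, ORT, ELM integrity loss, PED type and CST. The multivariable model then takes "as covariates all the variables with $p<0.10$ in the previous analysis". The test behind that p-value is not named. On reporting, the section says: "Results of logistic models will be presented in terms of beta coefficient and standard error, Odds Ratio and relative 95% Confidence interval and p-value". The one sensitivity analysis listed reweights for dropout and reuses the covariates already selected.

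On missing predictors, the candidate table says of lesion type that "UNG/P and UNG/Q will be considered as missing data", and a note adds that images from uncertified instruments go ungraded. On LOCF, section 1.1 says that "this approach will be maintained for the predictors to be included in the analysis of the primary endpoint". Section 1.1 also drops RECPAM, partly because 122 patients are too few for it, and drops the OCTA predictors because most values would be missing. Section 2 states the primary objective as the predictive value of early anatomical parameters.

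**The concern.** Section 3.5 supports 263 patients with two figures, a confidence interval width and a covariate limit. Only the first was updated. The only limit in the SAP is therefore about twice what its own rule gives for the patients available, and the SAP does not say whether a four-level variable counts as one covariate or three.

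The second part matters more. The protocol's RECPAM step carried some protection against overfitting: permutation-based choice of splits, pruning, and an AIC criterion justified by its equivalence to leave-one-out cross-validation. That went when RECPAM was dropped, and nothing replaced it. Choosing variables and estimating their effects on the same 122 outcomes tends to give coefficients that are too large and, for modest true effects, exaggerated odds ratios. Coefficients, confidence intervals and p-values computed as if the model had been fixed in advance do not show this. The stated objective is prediction, and the protocol's purpose is to judge whether these parameters could support the choice between q12w and q8w. An overstated model would bear directly on that.

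**Working it through.** **1. The plan's own figures.** Wald width = 2 × 1.96 × √(p(1−p)/n).
- n for a 12% width at p = 0.56: 1.96² × 0.56 × 0.44 / 0.06² = 262.9, so 263. Agrees.
- Width at n = 122, p = 0.50 (the maximum over 46% to 56%): 17.74%. Agrees.
- Limit of 12: the SAP cites rules of thumb without a divisor. Ten smaller-class patients per covariate gives 263 × 0.44/10 = 11.6 at 56% responders and 263 × 0.46/10 = 12.1 at 46%, both rounding to 12. Divisors of 15 or 20 do not reach 12 anywhere in the range. The ten is an inference.

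**2. The limit at 122.**
- Proportional scaling, which needs no divisor: 12 × 122/263 = 5.6.
- Ten per covariate: 122 × 0.44/10 = 5.4 (56%), 122 × 0.46/10 = 5.6 (46%), 122 × 0.50/10 = 6.1 (50%).
- If 5% of patients lack a covariate (115.9 evaluable): 5.1 to 5.8. If 20% (97.6 evaluable): 4.3 to 4.9. These loss rates are assumed; the documents give none, and LOCF will reduce the loss.

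**3. What could enter.** Seven variables at most. In coefficients, if every level is observed: lesion type 2, four change variables at 3 each, PED type 3, CST 1, so 2 + 12 + 3 + 1 = 18. If all seven were null and independent, the chance that at least one enters is 1 − 0.9⁷ = 52%.

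**4. Simulation of the screen.** Assumptions, none from the documents: CST (per SD) and one four-level variable associated with the outcome at the stated odds ratio, five noise variables; intercept logit(0.46); level frequencies 35/30/25/10%, lesion type 60/25/15%; one overall test per variable. There were 1,000 runs per cell, with the calibration slope taken on 20,000 new patients. Runs in which nothing was selected are excluded from the slope.

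Median calibration slope, Wald screen / likelihood-ratio screen:

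| True OR | Predictors | n = 122 | n = 263 |
|---|---|---|---|
| 1.3 | independent | 0.21 / 0.18 | 0.41 / 0.40 |
| 1.5 | independent | 0.43 / 0.38 | 0.65 / 0.64 |
| 2.0 | independent | 0.67 / 0.63 | 0.80 / 0.80 |
| 1.3 | latent correlation 0.3 | 0.25 / 0.22 | 0.40 / 0.40 |
| 1.5 | latent correlation 0.3 | 0.44 / 0.40 | 0.61 / 0.60 |
| 2.0 | latent correlation 0.3 | 0.61 / 0.58 | 0.72 / 0.72 |

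At OR 1.5 (independent) with 110 evaluable patients the slopes were 0.48 / 0.38, and with 98 they were 0.40 / 0.32. That the Wald value at 110 exceeds the one at 122 shows the simulation noise. A separately programmed likelihood-ratio version (independent predictors) gave 0.20, 0.41 and 0.62 at 122 against 0.40, 0.67 and 0.80 at 263.

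Median CST odds ratio when selected, n = 122 against 263: about 1.55 against 1.38 (true 1.3), 1.65 against 1.52 (true 1.5), about 2.07 against 2.01 (true 2.0).

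**5. How often the limit is passed at n = 122.** More than 5 variables: 0% of runs with independent predictors, at most 3.7% with correlated ones. More than 5 coefficients: 7% to 23% (independent), 13% to 60% (correlated).

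**6. How well a bootstrap corrects at n = 122** (200 datasets, 100 resamples each, screen repeated in each resample):

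| Scenario | AUC apparent / corrected / true | Slope corrected / true |
|---|---|---|
| OR 1.5, Wald | 0.66 / 0.56 / 0.60 | 0.55 / 0.45 |
| OR 1.5, likelihood ratio | 0.66 / 0.56 / 0.59 | 0.48 / 0.38 |
| OR 1.5, Wald, correlated | 0.69 / 0.59 / 0.60 | 0.55 / 0.43 |
| OR 2.0, Wald | 0.71 / 0.64 / 0.67 | 0.63 / 0.69 |

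**The case against.** Section 3.5 says nothing false: the 12 is tied to 263 patients and is never claimed for 122. If the unit is variables, the most that can enter is 7 against 5 to 6, and more than 5 hardly ever do, so the stale figure would seldom change an analysis. The SAP also adapted where the model is built. It dropped RECPAM and OCTA and reduced repeated measures to one change variable per parameter; a single pass over seven candidates is less data-driven than the protocol's stepwise selection across visits. All of this stands, and it makes the limit a minor correction.

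On validation, the protocol's estimand is summarised by odds ratios or beta coefficients and no risk score is planned, so a calibration slope may seem to measure something the trial does not produce. This does not carry the point. The stated objective is predictive value, and the selected odds ratios are themselves affected.

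On size, the simulation rests on assumed effects, and how an odds ratio of 1.5 is spread over four levels is a modelling choice. Much of the shrinkage is already there at 263. The part of the CST inflation due to the smaller sample at OR 1.5 is 1.65/1.52, about 9%, and it fades for strong effects. The slopes are conditional on something being selected; nothing was selected in roughly 10% to 19% of runs at OR 1.5 and 28% to 36% at OR 1.3 (n = 122, Wald screen, independent predictors). These limits stand. They bear on the exact values, not on the direction.

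**Conclusion.** The concern holds and should be fixed before the analysis is run. The arithmetic is firm: the limit for 122 is 5, at most 6, and lower if patients drop out of the model for a missing covariate. Taken alone that is a small omission.

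The substantive gap is a primary model for predictive value that is selected and estimated on the same 122 outcomes, with no plan to measure or report the resulting optimism. Over assumed true odds ratios of 1.3 to 2.0 the median slope runs from 0.18 to 0.67, against 0.40 to 0.80 at the planned size. The exaggeration of selected odds ratios is material for modest effects and small for strong ones. These sizes depend on assumed effects, level frequencies and correlation.

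**What to change.** In section 3.5, state the covariate limit for 122 (5, at most 6), recalculate it on the patients evaluable in the model, say whether it counts variables or coefficients, and report it if the selected model exceeds the limit.

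In section 6.3.1, keep the planned screen and model and add three things:
- name the test used for p<0.10, in particular for variables with several levels;
- report a bootstrap optimism-corrected c-statistic and calibration slope, repeating the screen in each resample, with a rule for resamples in which no variable passes;
- label the selected associations exploratory.

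Capping or collapsing candidates, or a penalised model, is optional. Ridge regression would not supply the standard errors, confidence intervals and p-values that 6.3.1 lists.

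The cost is SAP wording and some programming, with no new data or visits. The associations will look weaker, and at this sample size the correction is only approximate: in the simulated scenarios the corrected AUC fell somewhat below the truth, and the corrected slope erred in either direction.
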